### **Termination or Suspension of the Trial**

When for any reason the trial is terminated or suspended, the investigator shall notify the subjects promptly to that effect, and shall ensure that subjects receive appropriate medical treatment and post-treatment.

When the investigator terminates or suspends the trial, the investigator shall notify the director of the institution promptly and in writing to that effect, and shall provide a detailed written explanation for the termination or suspension.

**Completion of the Trial**

When the trial is completed, the investigator shall notify the director of the institution in writing to that effect, and report in writing an overview of the trial results.

**Storage of records**

The investigator shall retain essential documentation relating to the conduct of the trial in accordance with the directives of the director of the institution.

## APPENDIX H: Informed consent

### Time to obtain consent

The investigator or sub-investigator will obtain written consent by the trial subject prior to the commencement of study specific examination. Prior to the second implant, obtain consent to continuously participate in the clinical study from the subjects.

### Methods for explaining to trial subjects

The investigator (or sub-investigator) will give explanations to trial subjects. Study collaborators can give supplemental explanations.

The explanations should be given based on the explanation/consent document using terms which are the most easy to understand (non-technical terms). Questions made by trial subjects should be answered appropriately in the way the trial subjects can understand.

### Methods for obtaining consent

The investigator (or sub-investigator) who has given explanations will sign and date the consent document.

If any study collaborator has given supplemental explanations, the study collaborator will also sign and date the consent document. (Study collaborators are not allowed to solely give all necessary explanations to trial subjects.)

Supply the trial subject with the consent document and explanation document describing aforementioned necessary information and take sufficient time for the trial subject to decide whether or not he/she should participate in the clinical study.

Before obtaining consent, take sufficient time for the trial subject to sufficiently review the consent items and ask any questions. Answer the questions in a convincing manner.

Obtain the trial subject's spontaneous written consent to participate in the clinical study.

After obtaining the consent document signed and dated by the trial subject, the investigator (or sub-investigator) will enter the date of consent in the CRF and in the medical record. All consent documents must be retained.

Supply the trial subject with the copy (duplicate for the trial subject) of the consent document and the explanation document before the trial subject participates in the clinical study.

If the explanation document or consent document is subject to revision during the participation of the trial subject, follow the above procedures and re-obtain consent.

### Items mentioned for the written Informed Consent Form and other explanatory documents

The written Informed Consent Form and other explanatory documents must mention the following, at least.

The fact that the clinical study involves research.

The purpose of the trial.

The name and title of the investigator or sub-investigator, and how he or she can be contacted.

The trial method (including the aspects of the trial that are experimental, subject's inclusion/exclusion criteria, and when the trial is randomized, the probability of randomization for each treatment).

The expected clinical benefits, and the foreseeable risks or inconveniences to the subjects. (If any benefits for the subject will not be expected, it must be informed to the subject.)

When the persons to be enrolled as trial subjects are subjects, the availability of other medical treatments for their condition, and the potential major benefits and risks of such treatments as are available.

The expected duration of the subjects' participation in the trial.

That participation in the trial is voluntary; that the trial subject can refuse to participate in the trial or can withdraw from the trial at any time and that the subjects will not be disadvantaged or lose any benefit to which they are entitled if they refuse to enroll in the trial or if they withdraw from the trial after enrolling.

The handling of investigational product; if the subjects decied to diccontinue participation of clinical trial.

That the trial monitor, auditor, IRB, and regulatory authorities are allowed to examine the source data; that the confidentiality of the trial subjects will be protected when those data are examined by those persons; and that the subjects authorize the perusal of those data by those persons by sealing and/or signing the written consent form.

That the subjects' confidentiality will be protected even when the results of the clinical study are published.

The person in the study site conducting the trial whom the subjects should contact for further information about the trial or their rights, or if they develop a health problem associated with the trial.

The compensation and medical treatment the trial subjects can receive should they develop a health problem associated with the trial.

The number of subjects expected to be enrolled in the trial (including discrete variable).

That if information is received that may affect the wishes of the subjects regarding the subjects' ongoing participation in the trial, that information will be passed on promptly to the subjects.

The circumstances under which or the reasons subjects will be withdrawn from the trial.

The specifics about any expense the trial subjects will have to pay.

The specifics about any cash or the like that will be paid to the trial subjects (including the arrangement for calculating the sum to be paid).

Responsibilities of the trial subjects.

Information about Institutional review board.

Short Title:**Statistical Analysis Plan****ILH297-C003 /****NCT03090256****Full Title:****Statistical Analysis Plan****ILH297-C003****Protocol Title:**Clinical Investigation of the AcrySof® IQ PanOptix™ IOL
Model TFNT00**Project Number:**

A01875

Protocol TDOC Number:

TDOC-0052975

Author:**Template Version:**

Version 4.0, approved 16MAR2015

Approvals:

See last page for electronic approvals.

Job Notes:This is the first revision (Version 2.0) Statistical Analysis Plan for this study.

Executive Summary:**Key Objectives:**

To describe effectiveness and safety of the AcrySof IQ PanOptix Intraocular Lens (IOL) Model TFNT00 when implanted to replace the natural lens following cataract removal.

Decision Criteria for Study Success:

No formal decision criteria for study success are defined.

Table of Contents

Statistical Analysis Plan ILH297-C003	1
Table of Contents	3
List of Tables.....	4
List of Figures	4
No table of figures entries found.	Error! Bookmark not defined.
1 Study Objectives and Design.....	5
1.1 Study Objectives.....	5
1.2 Study Description	5
1.3 Randomization.....	6
1.4 Masking	6
1.5 Interim Analysis.....	6
2 Analysis Sets.....	6
2.1 Efficacy Analysis Sets	6
2.2 Safety Analysis Set	7
2.3 Pharmacokinetic Analysis Set	7
3 Subject Characteristics and Study Conduct Summaries	7
4 Effectiveness Analysis Strategy.....	7
4.1 Effectiveness Endpoints	7
4.2 Efficacy Hypotheses	9
4.3 Statistical Methods for Efficacy Analyses.....	9
4.4 Multiplicity Strategy.....	13
4.5 Subgroup Analyses and Effect of Baseline Factors.....	14
4.6 Interim Analysis for Efficacy	14
5 Safety Analysis Strategy	14
5.1 Safety Endpoints.....	14
5.2 Safety Hypotheses	15
5.3 Statistical Methods for Safety Analyses	15
5.3.1 Secondary Surgical Interventions Related to the Optical Properties of the IOL	15

5.3.2	Adverse Events (Including Secondary Surgical Interventions Not-Related to the Optical Properties of the IOL)	16
5.3.3	Device Deficiencies.....	17
5.3.4	Fundus Visualization	17
5.3.5	Intraocular Pressure	17
5.3.6	Slit Lamp Examination.....	17
5.3.7	Dilated Fundus Examination	18
5.3.8	IOL Observations.....	18
5.3.9	Subjective Posterior Capsule Opacification	18
5.3.10	Posterior Capsulotomy	18
5.3.11	Lens Decentration and Tilt	18
		18
5.3.13	Laser Flare Meter.....	19
		19
5.3.15	Problems during Surgery	20
5.4	Interim Analysis for Safety.....	20
6	Pharmacokinetic Analysis Strategy	20
7	Analysis Strategy for Other Endpoints	20
8	Sample Size and Power Calculations	20

1.1 Study Objectives

The objective of this study is to evaluate safety and effectiveness of AcrySof® IQ PanOptix™ IOL Model TFNT00 when implanted to replace the natural lens following cataract removal.

All analysis in this study will be performed for the descriptive purpose.

1.2 Study Description

This is a prospective, single-treatment, open-label and interventional clinical study. The investigational lens will be placed within the capsular bag after removal of the natural crystalline lens following phacoemulsification. Bilateral implantation of the investigational lens is planned for all subjects. The lens is implanted first to the eye with more advanced cataract. If both eyes have a similar degree of cataract, the surgery first for the right eye will be performed. The time of surgery for the remaining eye (2nd eye) will be within 30days from the first surgery which will be decided by the investigators based on the results of the examination and observation at Visit 1 (1-2 days after 1st eye implantation). Both eyes will be followed throughout the study. The 60 subjects (120 eyes) will be enrolled at 2 sites in Japan. A total of 10 scheduled visits are planned including the Preoperative/Visit 0 and the Operative Visit/Visit 00, Visit 00A. Scheduled postoperative visits must occur at the following intervals: 1-2 days, 7-14 days, 30-60 days and 120-180 days. See Table 1-1 Schedule of Study Visits.

Table 1-1 Schedule of Study Visits

Time from Implantation	Study Visit
Preoperative	Visit 0
Operative (Day 0)	Visit 00 / 00A
1-2 days	Visit 1 / 1A
7-14 days	Visit 2 / 2A
30-60 days	Visit 3 / 3A
120-180 days	Visit 4A

1.3 Randomization

This is a single-treatment study. All subjects will be implanted with AcrySof® IQ PanOptix™ IOL Model TFNT00 in both eyes.

1.4 Masking

This is an open label study.

1.5 Interim Analysis

No interim analyses are planned for this study.

2 Analysis Sets

2.1 Efficacy Analysis Sets

All Implanted Analysis Set (AAS):

All-Implanted Analysis Set (AAS) will include all eyes with successful test article implantation.

Best Case Analysis Set (BAS):

Best-Case Analysis Set (BAS) will include all eyes with successful test article implantation that had

- at least 1 postoperative visit;
- no macular degeneration at any time; and
- no major protocol violation

AAS and BAS will be used for primary effectiveness analysis. The primary analysis set for primary effectiveness analyses will be the AAS. [REDACTED]

[REDACTED]

[REDACTED]

2.2 Safety Analysis Set

The pre-treatment safety analysis set will include all subjects who consented to participate in the study. The pre-treatment safety analysis set will be the set that will be used to summarize occurrence of adverse experiences prior to exposure to the test article. The treatment-emergent safety analysis set will include all eyes with attempted implantation with the test article (successful or aborted after contact with the eye).

The treatment-emergent safety analysis set will be used for all safety variables after contact with the test article.

2.3 Pharmacokinetic Analysis Set

Not Applicable.

3 Subject Characteristics and Study Conduct Summaries

Subject characteristics and study conduct summaries include tables and listings such as a subject disposition table, demographics and baseline characteristics tables (including sex, age [<60 , $60-69$, $70-79$, ≥ 80], systemic complication [None/Yes, details] and past ocular surgery [None/Yes, details]), operation records*, summary of screen failures by reason and listing of subjects excluded from key analysis sets including reasons.

All descriptive summary statistics will be displayed with n and % for categorical data, and with mean, median, standard deviation, N, minimum, and maximum for continuous data.

Subject characteristics and study conduct summaries will be presented for the AAS (Overall and by site) and safety set (overall only). Subject characteristics and study conduct summaries for the BAS (overall and by site) will be presented if the total N excluded exceeds 10%.

[figure not shown]
* : Operative Eye, Problems During Surgery, Other Procedures at Surgery, Insertion Instrument, Incision Site, Final Incision Size, anterior capsulotomy size, and Lens Information.

4 Effectiveness Analysis Strategy

4.1 Effectiveness Endpoints

Primary effectiveness variables are as follows.

- Monocular photopic best corrected distance visual acuity (5 m)
- Monocular photopic distance corrected intermediate visual acuity (60 cm)
- Monocular photopic distance corrected near visual acuity (40 cm)

4.2 Efficacy Hypotheses

No formal hypothesis testing is planned.

4.3 Statistical Methods for Efficacy Analyses

Distance visual acuity (5 m), intermediate visual acuity (60 cm) and intermediate visual acuity (80 cm) will be categorized as follows.

- < 0.5
- $0.5 - < 0.7$
- $0.7 - < 1.0$
- $1.0 \leq$

Near visual acuity (40 cm) will be categorized as follows.

- < 0.4
- $0.4 \leq$

The N and percent of each category will be provided by visit. For these decimal visual acuity, descriptive statistics (geometric mean, dispersion factor (DF), N, median, min and max) will be provided by visit. Descriptive statistics (arithmetic mean, standard deviation, N, median, min and max) will also be provided for logMAR visual acuity by visit.

In order to compute the mean of decimal visual acuity correctly, the geometric mean must be used. The formulas for transforming from decimal acuity to logMAR score and back are as follows.

$$\text{LogMAR} = -\text{Log}_{10} (\text{Decimal Acuity})$$

$$\text{Decimal Acuity} = \text{antiLog} (-\text{LogMAR}) = 10^{-\text{LogMAR}}$$

The mean of decimal acuity is defined as

[figure not shown]
$$\text{Mean of Decimal Acuity} = 10^{\text{mean of} (-\text{Log MAR})} = 10^{\text{mean of} \text{ Log}_{10} (\text{Decimal Acuity})}$$

[figure not shown]
For geometric means, dispersion factors (DF) corresponds to standard deviations and defined as:

$$+DF = 10^{(\text{mean of } \log_{10}(\text{Decimal Acuity}) + \log(\text{SD}))} - 10^{\text{mean of } \log_{10}(\text{Decimal Acuity})}$$

$$-DF = 10^{(\text{mean of } \log_{10}(\text{Decimal Acuity}))} - 10^{(\text{mean of } \log_{10}(\text{Decimal Acuity}) - \log(\text{SD}))}$$

where, Log (SD) is a standard deviation of \log_{10} (Decimal Acuity).

4.4 Multiplicity Strategy

No hypothesis tests are planned.

4.5 Subgroup Analyses and Effect of Baseline Factors

Subgroup analyses for number and percentage of categorized primary endpoints as below will be conducted to assess the consistency of treatment effect across various subgroups.

Monocular photopic best corrected distance visual acuity (5 m) and Monocular photopic distance corrected intermediate visual acuity (60 cm)

- < 0.5
- $0.5 - < 0.7$
- $0.7 - < 1.0$
- $1.0 \leq$

Monocular photopic distance corrected near visual acuity (40 cm)

- < 0.4
- $0.4 \leq$

The consistency of the treatment effect of the primary endpoints will be assessed descriptively using summary statistics by category of the following subgroup factors:

- Age category (<60 , $60-69$, $70-79$, ≥ 80 years)
- Sex (Female, Male)
- Investigator

Also, 5m, 60cm and 40cm visual acuity from primary [REDACTED] effectiveness variables will be analyzed in the same manner by subgroup of photopic pupil size at Visit 4A (≤ 2.5 mm, $>2.5 - <4$ mm, ≥ 4 mm), retrospectively.

4.6 Interim Analysis for Efficacy

No interim analysis is planned for this study.

5 Safety Analysis Strategy

5.1 Safety Endpoints

The safety endpoints are:

- Secondary Surgical Interventions Related to the Optical Properties of the IOL

- Adverse Events (Including Secondary Surgical Interventions Not-Related to the Optical Properties of the IOL)
- Device Deficiencies
- Fundus Visualization
- Intraocular Pressure
- Slit Lamp Examination
- Dilated Fundus Examination
- IOL Observations
- Subjective Posterior Capsule Opacification
- Posterior Capsulotomy
- Lens Decentration and Tilt
- [REDACTED]
- Laser Flare Meter
- Subjective Symptoms
- Problems during Surgery

5.2 Safety Hypotheses

There are no formal safety hypotheses in this study. The focus of the safety analysis will be a comprehensive descriptive assessment of safety endpoints listed in Section 5.1.

5.3 Statistical Methods for Safety Analyses

Except otherwise stated, the analysis set for all safety analyses is the safety analysis set as defined in Section 2.2. Baseline will be defined as the last measurement prior to exposure to investigational product, except otherwise stated.

5.3.1 Secondary Surgical Interventions Related to the Optical Properties of the IOL

Secondary surgical intervention (SSI) will be recorded when secondary surgical intervention was performed. Number and percentage of eyes will be summarized for secondary surgical intervention related to the optical properties of the IOL at any post-operative visit where the

data are collected, separately for first implanted eye and second implanted eye. If secondary surgical intervention is performed, a subject listing that contains subject identification (investigator number, subject number) and visit will be provided, separately for first implanted eye and second implanted eye.

5.3.2 Adverse Events (Including Secondary Surgical Interventions Not-Related to the Optical Properties of the IOL)

The number and percentage of eyes with ocular adverse events (including secondary surgical interventions not-related to the optical properties of the IOL) will be presented. Also, the number and percentage of subjects with non-ocular adverse events will be presented. An eye with multiple ocular AEs of the same preferred term is only counted once toward the total of this preferred term. All information obtained on AEs will be displayed by subject.

Adverse events will be summarized in the following tables:

- All Adverse Events (Serious and Non-Serious Combined)
 - Ocular
 - Non-Ocular
- All Adverse Device Effects
 - Ocular
 - Non-Ocular
- All Serious Adverse Events (including Serious Adverse Device Effects)
 - Ocular
 - Non-Ocular
- Subject Listings
 - Non-Serious Ocular
 - Non-Serious Non-Ocular
 - Serious Ocular
 - Serious Non-Ocular

Also, patient listings will be provided for adverse experiences occurred from informed consent to exposure to the test article with pre-treatment safety analysis set.

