## 9.6 Safety Analysis

Patient listings will be provided for adverse experiences occurred from informed consent to exposure to the test article using Pre-Treatment Safety Analysis Set. Safety variables below will be analyzed using Treatment-Emergent Safety Analysis Set. For continuous variables, descriptive statistics (mean, standard deviation, N, median, min and max) will be provided for actual value and change from baseline at each visit. For categorical variables, N and percent will be provided for each category at each visit.

- Secondary Surgical Interventions related to the optical properties of the IOL
- Adverse Events (including secondary surgical interventions not-related to the optical properties of the IOL)
- Device Deficiencies
- Fundus visualization
- Intraocular Pressure
- Slit Lamp Examination
- Dilated Fundus Examination
- IOL Observations
- Subjective Posterior Capsule Opacification
- Posterior Capsulotomy
- Lens decentration and tilt
- [REDACTED]
- Laser Flare meter

- Subjective symptoms
- Problems during surgery

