## (1) General Information

### Definitions

**Device Deficiency** - any alleged deficiency related to the identity, quality, durability, reliability, safety, effectiveness, or performance of a device.

**Adverse Event (AE)** - any untoward medical occurrence in a subject, user, or other persons regardless of whether or not the event has a causal relationship with the medical device(s) or test procedure(s) in the study. Secondary surgical intervention is also reported as an adverse event (Additional information addressing adverse events is presented in Supplemental Attachment B: Definition of Adverse Events)

**Nonserious Adverse Event** - an adverse event that does not meet the criteria for a serious adverse event.

**Serious Adverse Event (SAE)** - an adverse event that led to any of the following:

- Death
- A serious deterioration in health that:
  - A) resulted in a life-threatening illness or injury.

*NOTE: Life-threatening means that the individual was at immediate risk of death from the event as it occurred, i.e., it does not include an event which hypothetically might have caused death had it occurred in a more severe form.*

- B) resulted in an any potentially sight-threatening event or permanent impairment to a body structure or a body function.
- C) required in-subject hospitalization or prolongation of an existing hospitalization.

*NOTE: Hospitalization that is standard of practice following a surgical procedure for the device type would not be a SAE. In general, hospitalization signifies that the individual remained at the*

*hospital or emergency ward for observation and/or treatment (usually involving an overnight stay) that would not have been appropriate in the physician's office or an out-patient setting. Complications that occur during hospitalization are AEs. If a complication prolongs hospitalization or fulfills any other serious criteria, the event is serious. When in doubt as to whether "hospitalization" occurred, the event should be considered serious.*

- D) resulted in a medical intervention to prevent A) or B) or any surgical intervention(excluding posterior capsulotomy).
- E) resulted in any indirect harm as a consequence of incorrect diagnostic test results when used within manufacturer's instructions for use.
- Fetal distress, fetal death, or a congenital abnormality or birth defect.

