**Adverse Device Effect** - any untoward and unintended response to a medical device (adverse device effect that cannot be denied the relations with the medical device), including any event resulting from device malfunction, insufficiencies or inadequacies in the instructions for use, or user error.

**Serious Adverse Device Effect** - an adverse device effect that has resulted in any of the consequences/characteristics of a serious adverse event or that might have led to any of these consequences if suitable action had not been taken or intervention had not been made or if circumstances had been less opportune.

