## APPENDIX A: Definition of Term

**Corneal edema** - Fluid in stromal layer of cornea with or without epithelial edema.

**Hyphema** - Blood in the anterior chamber, present over a period of time.

**Hypopyon** - Accumulation of white blood cells in the anterior chamber.

**Intraocular infection/Endophthalmitis** - Inflammation of ocular tissue including confirmed infection and sterile inflammation.

**Iritis** - Inflammation of the iris causing pain, tearing, blurred vision, small pupil (miosis), and a red congested eye, as evidenced by flare and/or cell in the anterior chamber.

**Lens Dislocation** – Displacement of the lens from its intended place.

**Macular degeneration** - Deterioration of macular tissue usually evident as a loss of pigment from the pigment epithelial layer. Included in this category are central serous chorioretinopathy, choroidal neovascular membrane and pigment epithelial detachment.

**Macular edema** - Swelling of macular tissue from excess fluid accumulation in the macular area diagnosed by clinical symptoms and/or fluoroscopic exam. This includes cystoid macular edema.

**Membrane formation on IOL** - Outgrowth of epithelial cells from the capsularhexis onto the surface of the IOL.

**Pigment precipitates on IOL** - Iris pigment deposits on the surface of the IOL.

**Pupillary block** - Blockage of normal aqueous flow through the pupil.

**Retinal detachment** - Separation of the retina from the pigment epithelium layer.

**Secondary Surgical Intervention** - Any secondary surgical procedure that can reasonably be expected to be IOL-related. This includes, but is not limited to, iridectomy for pupillary block, vitreous aspiration for pupillary block, repositioning of the lens, IOL removal for inflammation, and IOL replacement. This excludes posterior capsulotomy.

**Vitreous detachment** - Separation of vitreous gel from the retinal surface.

**Vitritis** – Inflammatory intraocular reaction (with clouding and cells) in the vitreous. Often accompanies inflammation of the ciliary body, iris, choroid, or retina. Can be sterile or due to infection.

**Raised IOP Requiring Treatment** - A persistent elevation of intraocular pressure secondary to cataract surgery that requires medical and/or surgical treatment.

**Synechiae** - Iris adhesion to adjacent ocular structures.

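### Are secondary surgical interventions related to the lens optics left out of the adverse event totals?

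*SAP*

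**What the plan says.** Protocol section 10(1) gives the reporting rule without a limit on cause: "Secondary surgical intervention is also reported as an adverse event". The same section treats as serious an AE that ends in a listed consequence, and criterion D extends that list to "or any surgical intervention(excluding posterior capsulotomy". Appendix A defines an SSI as "Any secondary surgical procedure that can reasonably be expected to be IOL-related" and does not divide SSIs by optical cause.

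The division appears in the analysis sections. SAP 5.1 lists "Secondary Surgical Interventions Related to the Optical Properties of the IOL" as one safety endpoint and AEs as the next. Protocol 9.6 describes the AE variable as "Adverse Events (including secondary surgical interventions not-related to the optical properties of the IOL". The heading of SAP 5.3.2 repeats that description, and so does its text, under which counts and percentages of eyes with "ocular adverse events (including secondary surgical interventions not-related to the optical properties of the IOL) will be presented". SAP 5.3.1 then counts eyes with an optics-related SSI, separately for first and second eyes, and adds a listing: "a subject listing that contains subject identification (investigator number, subject number) and visit will be provided".

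SAP 5.3.2 asks for tables of all AEs, all adverse device effects and all serious AEs, each split into ocular and non-ocular. It also asks for subject listings by seriousness and for everything recorded on AEs to be shown by subject. Neither document says in so many words whether an optics-related SSI also enters these tables.

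**The concern.** The definition covers all SSIs, but the description of the AE endpoint names only some of them. The limiting words recur in Protocol 9.6, SAP 5.1 and SAP 5.3.2, so they do not look like a stray slip. A programmer who asked what they are for could conclude that the two kinds of SSI are to be counted in different places, and could remove optics-related SSIs from the AE datasets.

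The totals in SAP 5.3.2 would then fall short of the events that Protocol section 10 defines as AEs and serious AEs, and would not reconcile with the event forms required by Protocol 10(3). The adverse device effect table could be short as well. The protocol describes such an effect as an "adverse device effect that cannot be denied the relations with the medical device", and a reoperation prompted by the lens optics is an obvious candidate. The listing specified in SAP 5.3.1 would not repair this, because it names neither seriousness nor relatedness. Safety is a stated objective, and the optic is the new feature of this lens, so these are events a reader would want to see classified.

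**Working it through.** The plan gives no SSI or serious AE rate, so there is no figure of its own to reproduce on this point. The check is a reading of the text, followed by a bound on the effect.

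**1. Which events become AE records.** Protocol 10(1) makes every SSI an AE, and Protocol 10(3) sends every AE to the AE form. An optics-related SSI is therefore in the AE data, with its own seriousness and relatedness.

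**2. What the tables draw on.** SAP 5.3.2 specifies tables of all AEs, all device effects and all serious AEs. Applied to the data in step 1, this includes optics-related SSIs. Leaving them out would need an extra selection step that neither document writes.

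**3. What the parenthesis does.** To name one kind of SSI as included is not to exclude the other. The words also have a function that fits the rest of the plan. Optics-related SSIs have a table of their own in SAP 5.3.1, and the remaining SSIs have none. The parenthesis tells the reader where to find the remaining ones. On this reading SAP 5.3.1 is a breakdown of a special-interest group, and SAP 5.3.2 agrees with Protocol section 10.

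**4. Serious AEs if the filter were applied anyway.** Under criterion D, an AE that results in surgery other than posterior capsulotomy is serious. The condition that prompted the reoperation is then a serious AE under its own term, and a filter on SSIs does not touch it. The ocular table counts eyes, so the eye stays in. The eye is lost only if the SSI is its sole serious AE record.

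**5. Size in that residual case.** Assume all 60 subjects (120 eyes) are in the treatment-emergent safety set, and that *k* eyes have an optics-related SSI as their only serious AE record. The values of *k* are assumed.

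Understatement of the ocular serious AE rate = *k* / number of eyes.

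| *k* | of 120 eyes | of 60 first (or second) eyes |
|---|---|---|
| 1 | 1/120 = 0.83 points | 1/60 = 1.67 points |
| 2 | 2/120 = 1.67 points | 2/60 = 3.33 points |
| 3 | 3/120 = 2.50 points | 3/60 = 5.00 points |

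The 60-eye column takes all *k* eyes to be in the same group. If the prompting condition is also recorded as an AE, every entry is zero.

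**6. Device effects.** Protocol section 10 defines an adverse device effect as a response to the device, and Protocol 10(3) leaves relatedness to the investigator. The underlying condition is the more natural entry in that table, and the SSI wording does not affect it. Appendix A's definition makes every SSI lens-related, so it does not single out the optics-related ones.

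**The case for a change.** The best case for a change is that the plan allows two readings and should allow one. Where the protocol wants a procedure left out it says so, as it does for posterior capsulotomy. It makes no such exception for optics-related SSIs, yet the analysis sections repeatedly describe something narrower. If the filter were applied, a reader could not rebuild the totals by adding SAP 5.3.1 to SAP 5.3.2, because an eye could appear in both and the first is split by eye order while the second states no split. The listing in SAP 5.3.1 is also thinner than several others in the SAP.

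Part of this stands. No sentence settles the matter expressly, and a footnote to the AE tables would do no harm. But the absence of an exception for optics-related SSIs supports inclusion: with no exclusion written, the general rule in Protocol section 10 governs. The thin listing matters little, because the serious and non-serious ocular listings in SAP 5.3.2 carry the same events with their classification. That information is lost only if the unwritten filter is applied to the listings too.

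**Conclusion.** The concern identifies loose wording, not a fault in the analysis. Followed as written, the plan records all SSIs as AEs, tabulates all AEs, and counts the optics-related SSIs once more by eye in SAP 5.3.1. Under-counting would need a programmer to add an exclusion found in neither document, against tables specified as covering all events. Even then the ocular serious AE rate would move by 0.83 points per affected eye on 120 eyes (1.67 on 60), and only for an eye with no other serious AE record. The affected eyes would still be counted in SAP 5.3.1.

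The study is single-arm and descriptive, with no hypotheses or success criteria, so no decision depends on these totals. This is a gap that analysts can be expected to fill sensibly, and a revision would only put the more direct reading into words. The conclusion rests on investigators recording SSIs as AEs, as Protocol section 10 requires. The sizes rest on an assumed full set of 120 eyes and on assumed event counts.
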